3.3 Patient information and consent

It is the responsibility of the investigator to give each patient, prior to any study-related activities, full and adequate verbal and written information regarding the objective and procedures of the study and the possible risks involved. The patients must be informed about their right to withdraw from the study at any time. The written patient information and/or ICF must not be changed without prior discussion with Sobi. Before any revisions are implemented, the revised written patient information and/or ICF must be approved by the IEC/IRB.

It is the responsibility of the investigator to obtain signed informed consent from all patients prior to any study-related activities. The patients should receive a copy of the written information and the signed ICF.

4 **Introduction**

4.1 Background

AIHA is defined as the increased destruction of RBCs in the presence of anti-RBC autoantibodies, with or without complement activation. Autoantibodies are produced by both tissue and circulating self-reactive B lymphocytes, following cooperation with T-helper lymphocytes. A third key player in anti-RBC autoimmunity is the complement system, which can induce a direct erythrocyte osmotic lysis through the sequential activation of the membrane attack complex or an extravascular hemolysis through Ab-dependent cellular cytotoxicity and phagocytosis occurring preferentially in the spleen and lymphoid organs [3].

AIHA occurs uncommonly with estimates of 1 to 3 in 100 000 population annually. The ability of the autoantibody to bind to the erythrocyte antigen at specific temperatures is fundamental to the diagnosis in terms of whether it is designated as warm (reacts maximally at 37 °C) or cold (reacts maximally at 4 °C) AIHA. The pathologic and clinical features of AIHA relate to the autoantibody class, thermal amplitude and their efficiency in activating complement [4].

AIHAs consist of warm-, cold-, and mixed-reactive Ab types that are directed against antigens on the RBC surface. The autoantibodies may be idiopathic (primary) or related to an underlying condition such as infection, malignancy, or immune disease (secondary) [5]. Cold-antibody AIHAs are further characterized into CAD, whose patients will be focused on this study.

4.1.1 Cold agglutinin disease and unmet medical need

Primary chronic CAD is an uncommon form of AIHA in which hemolysis is thought to be entirely complement-dependent. CAD accounts for about 15 % of AIHAs and is defined as an AIHA mediated by cold agglutinins, without any obvious underlying disease such as aggressive lymphoma, other overt malignancies or specific infections. Cold agglutinins are autoantibodies that can agglutinate RBCs at an optimum temperature of 3 to 4 °C [6].

Cold antibodies (IgM) temporarily bind to the RBC membrane, which in turn activates complement, and leads to the deposition of C3b on the cell surface. These C3b-coated RBCs are cleared slowly by the macrophages of the liver through extravascular hemolysis. To a lesser extent, the complete complement cascade may be activated at the cell surface, ultimately resulting in the insertion of membrane attack complex C5b to C9 and intravascular hemolysis.

Various therapeutic approaches have been used in treating these patients, including RBC transfusions, off-label use of rituximab, rituximab-based combination therapy or bortezomib [7]. However, a substantial unmet medical need still exists.

4.1.2 Summary of clinical experience with pegcetacoplan

Clinical data from studies with pegcetacoplan in patients with PNH indicate that pegcetacoplan is an effective complement modulating agent resulting in broad control of intravascular and extravascular hemolysis.

To date, pegcetacoplan, at doses of \leq 360 mg/day, has been well tolerated when administered via s.c. infusion, including to patients with warm AIHA and CAD (Study APL2-CP-AIHA-208 [8]; see Section 4.1.2.1).

Available safety data from completed and ongoing clinical studies have not indicated any serious safety concern in patients treated with pegcetacoplan.

Please refer to the latest version of the pegcetacoplan IB for the overall risk-benefit assessment and the most accurate and current information regarding the drug metabolism, PK, efficacy and safety of pegcetacoplan.

4.1.2.1 Study APL2 CP AIHA-208

This was a phase 2, open-label, prospective pilot study of pegcetacoplan conducted in subjects with a primary diagnosis of warm AIHA or CAD in parallel [8]. The study included 24 patients, 11 patients with a primary diagnosis of warm AIHA in Cohort 1 and 13 patients with a primary diagnosis of CAD in Cohort 2. Patients in each cohort were to be randomly (1:1) assigned to receive either 270 mg/day or 360 mg/day of pegcetacoplan treatment for up to 12 months (Part A, the core study phase). Seven patients in Cohort 1 (warm AIHA) and 10 patients in Cohort 2 (CAD) completed the study per the protocol.

Safety data demonstrated the tolerability of pegcetacoplan; s.c. pegcetacoplan was well tolerated in both cohorts. Most TEAEs were mild, and most (81 %) were deemed by the principal investigator to be unlikely related/unrelated to study drug. No SAEs were considered related to pegcetacoplan. The most common possibly treatment-related TEAE in Cohort 2 (CAD) was headache, reported in 3 patients (23.1 %).

Antidrug antibody responses observed in the study had no noticeable impact on the PK/PD, efficacy, or safety profile of pegcetacoplan.

This study also demonstrated that pegcetacoplan rapidly increased Hb values, an effect that persisted for 48 weeks. This result was more prominent in patients with CAD (Cohort 2). In addition, transfusion avoidance during the 12 months of the core study phase was observed in Cohort 2 in 77 % of patients after treatment with pegcetacoplan. Improvements in hemolysis by reduction in ARCs, LDH and indirect bilirubin were observed in both cohorts.

Persistent inhibition of the alternative complement pathway was demonstrated without affecting classical complement activation. Increases in C3 levels were also observed in both dosage groups (270 mg/day and 360 mg/day). There was also a trend of reduction of C3 deposition on RBCs (% Type I) in both cohorts, which suggests that pegcetacoplan protects RBCs from complement-mediated attack.

Serum pegcetacoplan concentrations reached steady state between Week 4 and Week 8. After reaching steady state, mean trough concentrations of pegcetacoplan were generally higher in the 360 mg/day group, supporting that exposure increased in a dosage-dependent manner.

In summary, pegcetacoplan produced consistent, meaningful, and prolonged effects on most relevant clinical efficacy measures along with an acceptable safety profile in patients with warm AIHA and CAD.

4.2 Study rationale

Aberrant complement pathway activation has been demonstrated in many autoimmune disorders, particularly in diseases associated with pathogenic autoantibodies [9]. Binding of C1 complex, the triggering mechanism of the CP, to an immune complex containing a self-antigen and an autoantibody results in the formation of the CP C3 convertase, C4b2a. Subsequent cleavage of

complement proteins C3 and C5 results in generation of C3a and C5a, anaphylatoxins that attract and activate effector immune cells to the site of Ab binding/complement activation; deposition of C3 opsonins that mediate phagocytosis and lymphocyte activation and, finally, the formation of the membrane attack complex, a lytic pore that disrupts the cellular membrane and leads to cellular destruction [10]. Thus, complement components have long been an attractive target for drug development.

Pegcetacoplan, the active ingredient in pegcetacoplan solution for s.c. infusion 1080 mg/20 mL, is a pentadecapeptide (a bioactive cyclic tridecapeptide C3-inhibiting moiety and a 2-amino acid linker) covalently coupled to each end of a linear 40-kDa PEG chain, so that there are 2 active peptide moieties per molecule of pegcetacoplan. The peptide portion of the drug binds to complement C3 and is a broad modulator of the complement cascade, a biological process that is part of innate immunity and is involved in multiple inflammatory processes. The PEGylation of the molecule imparts slower elimination from mammalian systems following administration (see the pegcetacoplan IB).

On the basis of scientific and clinical evidence on the role of complement activation in CAD, it can be concluded that pegcetacoplan, which acts through modulation of the complement system, has the potential to prevent C3-mediated extravascular and intravascular hemolysis in CAD patients.

Pegcetacoplan was able to rapidly increase Hb values in 10 patients with CAD treated in the phase 2 APL2 CP AIHA-208 study, reducing both intravascular and extravascular hemolysis (as shown by reduction and normalization of LDH, indirect bilirubin and ARCs) and leading to transfusion independency in the majority of them, being well tolerated.

Thus, this phase 3 study is being conducted to confirm the safety and efficacy of pegcetacoplan in patients with CAD.

Pegcetacoplan will be compared to placebo in a double-blinded, randomized fashion. The treatment duration will be 24 weeks for both treatment groups to ensure capturing a durable treatment effect. At the end of the randomized portion of the study, all enrolled patients will be offered a 24-week treatment with pegcetacoplan in an open-label fashion, and 48 additional weeks to allow treatment continuity until the product is commercially available.

4.3 Potential risks and benefits

Cumulatively, up to 10 July 2021, 342 subjects have been systematically exposed (via intravenous and s.c. route) to pegcetacoplan in completed and ongoing studies across multiple indications. The administration of pegcetacoplan was well tolerated and the safety data did not indicate any significant safety concern. Nonetheless, a number of safety monitoring practices are being employed by this protocol to ensure patient safety, including physical examination, vital signs monitoring, ECGs, hematology (including coagulation), serum chemistry, urinalysis and prompt reporting of AEs.

As with other complement-inhibiting drugs, there is a potential increased risk of infections with encapsulated pathogens including *Streptococcus pneumoniae*, *Neisseria meningitidis* (serogroups A, C, W, Y, and B), and *Haemophilus influenzae* Type B. There have been no reports of meningococcal infection or other severe infections potentially related to encapsulated bacteria through 334.5 person-years of systemic pegcetacoplan exposure. The serious infections that were observed across studies were manageable and did not require discontinuation from pegcetacoplan. Therefore, the sponsor believes that the data do not support an increased risk of serious infections attributable to pegcetacoplan treatment.

Thus, patients will be required to have documented evidence of vaccination against these pathogens within 2 years before study initiation, or will be required to receive vaccination upon initiation of IMP.

To receive treatment with IMP, patients who are documented nonresponders to vaccination or cannot be vaccinated prior to IMP initiation must receive prophylactic antibiotics according to the local standard practices.

Body temperature and other vital signs will be monitored at all clinic visits, and relevant blood parameters will be monitored throughout the study to assess for signs of infection. Patients will be provided with emergency study cards that list symptoms associated with infections caused by encapsulated organisms. This study card also guides patients with instructions to contact their study physician or seek emergency medical care in the event they experience any of the listed symptoms. In the event of a suspected infection, the principal investigator should provide guidance on appropriate action to be taken.

Infusion-site/pump safety will be assessed during clinical visits, and any significant finding from the assessment will be reported as an AE (see Section 6.5.4.1).

Hemolysis occurring in study subjects after sudden pegcetacoplan withdrawal has been observed in 2 patients with PNH. Abrupt discontinuation of pegcetacoplan treatment may render PNH red blood cells unprotected against complement activation, potentially resulting in hemolysis leading to severe anemia.

Whenever possible, the study medical monitor will be contacted before interrupting or discontinuing treatment with IMP.

4.3.1 COVID-19 risk mitigation measures

The sponsor is not currently aware of any evidence associating pegcetacoplan use with specific risks or complications of COVID-19. The sponsor recognizes the need to consider the public health risks of the COVID-19 pandemic within the context of conducting a clinical study. Because these risks may change as the pandemic evolves and may vary on the basis of geographic location, the sponsor will continue to evaluate the risk-benefit around study conduct on an ongoing and patient-by-patient basis.

In the event that an investigative site is closed or a patient is unable/unwilling to attend a study visit because of COVID-19 restrictions and, in the opinion of the investigator, it is in the patient's best interest to continue in the study, the following mitigation measures may be implemented for the study and utilized if deemed necessary and authorized by the sponsor, including but not limited to:

- In locations where home nursing services may be utilized, a home nursing vendor may be set up to complete assessments at a patient's home.
- Collection of AEs or SAEs should be done over the phone and documented in the source documents and in the correct eCRF page.
- If a patient has been tested for COVID-19, the results, if available, will be documented in the eCRF.
- Minimized schedule of assessment can be followed during COVID-19 restrictions (Table 5 and Table 6), including the use of certified local laboratory.
- The EDC system will capture any missed assessments related to COVID-19.
- Where applicable, relevant study documentation will be updated and communicated to Health Authorities and/or IRBs/IECs as required.

COVID-19 vaccination is permitted during the course of the study as per local standard of care. Details of the deployed vaccine should be recorded in the medical notes and study visits should continue as planned if possible and appropriate.

5 Study objectives and endpoints

5.1 Primary objective

The primary objective of this study is to demonstrate the efficacy of twice-weekly s.c. 1080-mg infusions of pegcetacoplan compared with that of placebo in patients with CAD.

5.1.1 Primary endpoint

The primary efficacy endpoint is response to treatment at Week 24.

Response is defined as:

- An increase in Hb of ≥ 1.5 g/dL from Baseline or Hb normalization at Week 16; AND
- Maintenance of this effect from Week 16 to Week 24; AND
- The absence of PRBC transfusions (between Week 5 and Week 24).

Note: Hb normalization is defined as within normal range (between the defined ULN and LLN), as set by the testing laboratory.

5.2 Secondary objectives

The following are the key secondary objectives of this study:

- To demonstrate the effect of pegcetacoplan on the number of PRBC transfusions in patients with CAD.
- To demonstrate the effect of pegcetacoplan on health-related quality of life in patients with CAD.

The following are the other secondary objectives of this study:

- To assess the effect of pegcetacoplan on clinical laboratory markers of hemolysis and transfusion dependence in patients with CAD.
- To determine the durability of response in patients with CAD receiving pegcetacoplan.
- To assess tolerability, safety and immunogenicity of pegcetacoplan in patients with CAD.
- To describe long-term effect of pegcetacoplan in patients with CAD.

5.2.1 Secondary endpoints supporting the secondary objectives

5.2.1.1 Key secondary efficacy endpoints

The following are the key secondary endpoints for this study:

- Change from Baseline to Week 24 in Hb level.
- Transfusion avoidance (Yes/No) from Week 5 to Week 24.
- Change from Baseline to Week 24 in the FACT-An score.

5.2.1.2 Secondary efficacy endpoints

The secondary efficacy endpoints are as follows:

Part A:

- Number of PRBC transfusions from Week 5 to Week 24.
- Change from Baseline to Week 24 in the following:
 - LDH level.
 - Haptoglobin level.
 - Indirect bilirubin level.
 - ARC.
 - D-dimer level.
- Normalization of markers of hemolysis at Week 24, specifically:
 - LDH level.
 - Indirect bilirubin level.
 - ARC.

- Time to first normalization from Baseline to Week 24 for the following:
 - Hb level.
 - LDH level.
 - Indirect bilirubin level.
 - ARC.
- Number of PRBC units transfused from Week 5 to Week 24.
- Change from Baseline to Week 24 in the following:
 - FACIT-F subscale score of the FACT-An scale.
 - SF-12 score.
 - EQ-5D-5L score.

Part B:

- Change from Baseline to Week 48 in the following:
 - Hb level.
 - LDH level.
 - Haptoglobin level.
 - Indirect bilirubin level.
 - ARC.
 - D-dimer level.
- Normalization of markers of hemolysis at Week 48, specifically:
 - LDH level.
 - Indirect bilirubin level.
 - ARC.
- Durability of response for patients randomized to pegcetacoplan who achieve the primary endpoint at Week 24.
- Change from Baseline to Week 48 in the following:
 - FACT-An score.
 - FACIT-F subscale score of the FACT-An scale.
 - SF-12 score.
 - EQ-5D-5L score.

5.2.1.3 Tertiary efficacy endpoints

The tertiary efficacy endpoints are as follows:

Part C:

- Change from Baseline to Week 96 in the following:
 - Hb level.
 - LDH level.
 - Haptoglobin level.
 - Indirect bilirubin level.
 - ARC.

- D-dimer level.
- Normalization of markers of hemolysis at Week 96, specifically:
 - LDH level.
 - Indirect bilirubin level.
 - ARC.
- Change from Baseline to Week 96 in the following:
 - FACT-An score.
 - FACIT-F subscale score of the FACT-An scale.
 - SF-12 score.
 - EQ-5D-5L score.

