^x If the screening period is extended beyond 4 weeks, in addition to the regular Baseline serum chemistry to be analyzed in the central laboratory, a local safety serum chemistry sample including at least BUN, creatinine, ALT, AST, alkaline phosphatase, GGT, bilirubin (total, direct and indirect), chloride, sodium, potassium, phosphorus, calcium and glucose should be obtained up to 7 days before dosing and ensured to be available to the investigator before first IMP dosing. This sample is only obtained to ensure continued safety of dosing, and only the results of the central laboratory evaluation will be considered in the general study evaluation.

^y The use of the local laboratory is allowed for the baseline pregnancy tests to ensure that results are available prior to dosing on Day 1.

^z Baseline health-related quality of life assessments will be performed prior to dosing on Day 1 (if convenient for the patient and/or the site due to logistic reasons, Baseline assessments may be performed the day before first IMP dosing).

Note: Unscheduled additional visits may be performed at the investigator's judgment. Any of the study procedures or other assessments may be performed at the unscheduled visit at the discretion of the investigator.

Table 2 Schedule of assessments: Part B, Part C and Follow-up period

Study Period	Part B:			Part C:					Follow-up period ^o	
	Open-label treatment period			Open-label maintenance period					EOT/ET	EOS
Study Week	32	40	48	56	64	72	80	88	96	104
Study Day	225	281	337	393	449	505	561	617	673	729
Study Visit	11	12	13	14	15	16	17	18	19	20
Visit window (\pm days)	7	7	7	7	7	7	7	7	7	7
RBC transfusions collection	X	X	X	X	X	X	X	X	X	X
Prophylactic antibiotic administration ^a	According to local standard practices in patients who cannot be vaccinated									
Full physical examination (including weight) ^b									X	X
Brief physical examination (including weight) ^c	X	X	X	X	X	X	X	X		
12-lead ECG (prior to venipuncture)	X								X	X
IMP administration ^d	Twice weekly-----→			Twice weekly-----→						
Infusion-site assessment ^e	X	X	X	X	X	X	X	X		
Concomitant medications/treatments	X	X	X	X	X	X	X	X		X
Vital sign measurements ^f	X	X	X	X	X	X	X	X		X
Urine studies	X	X	X	X	X	X	X	X		X
Blood ^g										
Pharmacokinetics ^h	X	X	X	X		X			X	X
Anti-pegcetacoplan peptide and anti-PEG Ab assay ⁱ	X	X	X	X		X			X	X
Hematology	X	X	X	X	X	X	X	X		X
Serum chemistry	X	X	X	X	X	X	X	X		X
Coagulation profile ^k	X	X	X	X	X	X	X	X		X

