^d Patients will self-administer s.c. IMP, after receiving appropriate training by research personnel. Dosing diaries will be used for study treatment and are to be completed for each dose administered at the clinic or at home. On dosing days that coincide with clinic visits, doses will be administered at the clinic visit.

^e Between site visits, patients will be instructed to report any infusion-site reaction to the study coordinator.

^f On clinic dosing days, vital signs will be measured within 2 hours before dosing and venipuncture (and ECG, if applicable), and at 30 minutes (\pm 5 minutes) post dose (see Section 6.5.4.4).

^g If IMP is administered at study visit, blood samples will be taken before dosing.

^h PK samples will be taken within 15 minutes before the administration of the study drug at each visit and strictly before the start of dosing.

ⁱ For patients with positive anti-pegcetacoplan peptide or anti-PEG Ab in last dose samples, additional samples will be collected every 6 months from last dose until Ab levels returns to baseline.

^k The use of silica reagents in coagulation panels should be avoided in all patients.

^m Serum samples for immunoglobulins quantitative and CAD titer assessment to be kept at 37 °C to 38 °C (until serum has been removed from the clot, after which the sample can be handled at room temperature).

ⁿ Urine pregnancy test will be completed for WOCBP every 4 weeks, using a home test if there is no clinic visit. Urine pregnancy test to be performed prior to dosing on days where dosing coincides with clinic visits.

^o After completion of the maintenance period, patients will complete an EOT visit. Patients who discontinue early should complete an ET visit. An EOS visit will be performed 8 weeks (\pm 7 days) after treatment discontinuation for any reason.

Note: Unscheduled additional visits may be performed at the investigator's judgment. Any of the study procedures or other assessments may be performed at the unscheduled visit at the discretion of the investigator.

2 Abbreviations and definition of terms

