6.3.3 Withdrawal of patients from treatment or study

6.3.3.1 Withdrawal from treatment

A patient should be withdrawn from the study treatment if, in the opinion of the investigator, it is medically necessary, or if it is the wish of the patient. Specific treatment stopping criteria are provided in Section 6.4.7.

When a patient is withdrawn from treatment, the study site must immediately notify the study medical monitor, and the date of last IMP dose and the date and reason for treatment withdrawal should be clearly described in the relevant sections of the eCRF. If a patient is removed from treatment because of an AE, the reason for treatment withdrawal should always be stated as 'adverse event' irrespective of whether this was the investigator's or the patient's decision.

The patient will continue to participate in the study without taking study treatment. Patients who stop study treatment prior to the exit visit should undergo all follow-up visits and procedures through study completion, unless they are unwilling or unable or consent has been withdrawn. Patients who wish to fully withdraw from the study before completion should be encouraged to complete the Early termination visit (see Table 2).

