^y The use of the local laboratory is allowed for the baseline pregnancy tests to ensure that results are available prior to dosing on Day 1.

^z Baseline health-related quality of life assessments will be performed prior to dosing on Day 1 (if convenient for the patient and/or the site due to logistic reasons, Baseline assessments may be performed the day before first IMP dosing). Note: Unscheduled additional visits may be performed at the investigator's judgment. Any of the study procedures or other assessments may be performed at the unscheduled visit at the discretion of the investigator.

Table 6 Revised COVID-19 minimum schedule of assessments: Part B, Part C and Follow-up period

Study Period	Part B: Open-label treatment period			Part C: Open-label maintenance period					Follow-up period ^p	
	EOT/ET	EOS								
Study Week	32	40	48	56	64	72	80	88	96	104
Study Day	225	281	337	393	449	505	561	617	673	729
Study Visit	11	12	13	14	15	16	17	18	19	21
Visit window (\pm days)	7	7	7	7	7	7	7	7	7	7
RBC transfusions collection	X	X	X	X	X	X	X	X	X	X
Prophylactic antibiotic administration ^a	According to local standard practices in patients who cannot be vaccinated									
Full physical examination (including weight) ^b									X	X
Brief physical examination (including weight) ^c	X	X	X	X	X	X	X	X		
12-lead ECG (prior to venipuncture)	X								X	X
IMP administration ^d	Twice weekly-----→			Twice weekly-----→						
Infusion-site assessment ^e	X	X	X	X	X	X	X	X	X	
Concomitant medications/treatments	X	X	X	X	X	X	X	X	X	X
Vital sign measurements ^f	X	X	X	X	X	X	X	X	X	X
Urine studies	X	X	X	X	X	X	X	X	X	X
Blood ^g	X	X	X	X	X	X	X	X	X	X
Pharmacokinetics ^h	X	X	X	X		X			X	X
Anti-pegcetacoplan peptide and anti-PEG Ab assay ⁱ	X	X	X	X		X			X	X
Hematology	X	X	X	X	X	X	X	X	X	X
Serum chemistry	X	X	X	X	X	X	X	X	X	X
Coagulation profile ^k	X	X	X	X	X	X	X	X	X	X
TNF α , IL-6, IL-10, IFN γ and IL-1 β	X	X	X						X	X

Table 6 Revised COVID-19 minimum schedule of assessments: Part B, Part C and Follow-up period

Study Period	Part B:			Part C:					Follow-up period ^p	
	Open-label treatment period			Open-label maintenance period					EOT/ET	EOS
Study Week	32	40	48	56	64	72	80	88	96	104
Study Day	225	281	337	393	449	505	561	617	673	729
Study Visit	11	12	13	14	15	16	17	18	19	21
Visit window (\pm days)	7	7	7	7	7	7	7	7	7	7
Complement profile (C3, functional assays for classical and alternative complement pathways)	X	X	X						X	X
Flow cytometry for C3 deposition on RBCs	X	X	X						X	X

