## 7.5 TERTIARY EFFICACY ENDPOINT ANALYSIS FOR PART C

All tertiary efficacy analyses will be analyzed with the ITT set and data presentations will be by visit and by randomized treatment group in Part A as well as combined.

The change from Baseline at Week 96 in Hb, LDH, haptoglobin, indirect bilirubin, ARC and D-dimer will be analyzed using descriptive statistics.

For the endpoint regarding the normalization of markers of hemolysis (LDH, indirect bilirubin and ARC), at Week 96, the number and percentage of patients who respond will be tabulated in frequency tables by randomized treatment group in Part A as well as combined.

The change from Baseline at Week 96 in FACT-An, SF-12, EQ-5D-5L and FACIT-F subscale score of the FACT-An scale will be analyzed using descriptive statistics.

All data will be used as collected (no ICES will be considered) and no imputations will be done.

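### Table 2, as extracted, leaves the laboratory and urine rows blank at the Week 96 EOT/ET visit, in conflict with Table 6 and with six descriptive Week 96 endpoints

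*Protocol*

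**What the plan says.** Protocol Section 5.2.1.3 sets the Part C endpoints, beginning "Change from Baseline to Week 96 in the following" and listing Hb, LDH, haptoglobin, indirect bilirubin, ARC and D-dimer. SAP Section 7.5 keeps them: "The change from Baseline at Week 96 in Hb, LDH, haptoglobin, indirect bilirubin, ARC and D-dimer will be analyzed using descriptive statistics".

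Protocol Section 6.5.4.2 sends sites to Tables 1 and 2 for the timing of laboratory samples. Its Table 4 puts Hb and ARC under hematology; LDH, haptoglobin and bilirubin under serum chemistry; and D-dimer under coagulation.

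Table 2 has ten visit columns: "Study Week 32 40 48 56 64 72 80 88 96 104". Week 96 is the EOT/ET visit and Week 104 the EOS visit. The hematology row carries nine marks, "Hematology X X X X X X X X X", and so does the chemistry row, "Serum chemistry X X X X X X X X X". In both, the empty cell is the one under Week 96. In Table 6 (Appendix 5) the hematology row has ten: "Hematology X X X X X X X X X X".

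The early termination visit also follows Table 2. Section 6.3.3.1 says that patients leaving the study "should be encouraged to complete the Early termination visit (see Table 2"), and Table 2 footnote o says "Patients who discontinue early should complete an ET visit".

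**The concern.** The plan analyses a Week 96 change in six laboratory variables, but the table that governs sampling shows no draw for any of them at Week 96. The table meant to shorten visits under COVID-19 restrictions asks for more at that visit than the full schedule does. Both cannot be right.

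Two things are at stake. The first is whether the six Week 96 changes can be computed at all. The second is the safety laboratory record at the end of treatment, whenever a patient stops, because the same column serves as the ET visit. Safety endpoints in Section 5.2.1.4 include laboratory abnormalities up to 8 weeks after EOT. Without an EOT sample, the EOS result has no on-treatment value close to the last dose to compare with.

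**Working it through.** No sample-size or power figure bears on this point. The check is a cell count and a comparison of passages.

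**1. Cell count.** Each row below was read against the ten visit columns; Week 96 is the ninth (Day 96 × 7 + 1 = 673).

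| Row | Table 2: Weeks 32–88 / 96 / 104 | Table 6: Weeks 32–88 / 96 / 104 |
|---|---|---|
| Hematology | 8 / blank / 1 | 8 / 1 / 1 |
| Serum chemistry | 8 / blank / 1 | 8 / 1 / 1 |
| Coagulation | 8 / blank / 1 | 8 / 1 / 1 |
| Urine studies | 8 / blank / 1 | 8 / 1 / 1 |
| Vital signs | 8 / blank / 1 | 8 / 1 / 1 |
| Concomitant medications | 8 / blank / 1 | 8 / 1 / 1 |
| Infusion-site assessment | 8 / blank / blank | 8 / 1 / blank |

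Seven rows differ between the tables, all in the Week 96 cell and nowhere else.

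**2. Is the column intact?** In the same part of Table 2, the RBC transfusion, full physical examination, ECG, PK and antibody rows keep their Week 96 mark. On the continuation page FACT-An, SF-12 and EQ-5D-5L keep it too. The column has not dropped out as a whole.

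**3. Which endpoints depend on the blank rows?** By Table 4: hematology 2 (Hb, ARC), chemistry 3 (LDH, haptoglobin, indirect bilirubin), coagulation 1 (D-dimer). 2 + 3 + 1 = 6, which is every Week 96 laboratory change endpoint. The urine row affects safety only.

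**4. Does other text supply the assessment?**
- Vital signs: Section 4.3 has them monitored at all clinic visits, although Section 6.5.4.4 points back to Tables 1 and 2.
- Concomitant medications: Section 6.4.10.1 documents them through the EOS visit.
- Infusion site: Section 6.5.4.8 asks for an assessment on clinic-visit days.
- Laboratory and urine: no passage schedules them at a completed Week 96 visit. Table 6 applies only during COVID-19 restrictions. Section 6.3.3.2 asks in general terms for relevant samples when a patient withdraws from the study, which covers part of the ET case.

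**5. Spacing if Table 2 is followed literally.** The scheduled laboratory samples on either side of EOT are Week 88 (Day 617) and Week 104 (Day 729): 729 − 617 = 112 days. The last on-treatment sample is 673 − 617 = 56 days before EOT, and the next is 729 − 673 = 56 days after it. SAP Section 5.2.3 gives Week 96 no analysis window, so the windowing rule offers no way for the Week 88 sample to stand in.

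**6. What survives early termination?** SAP Section 1.1 drops normalization analyses beyond Part A, so the three Week 96 normalization endpoints (LDH, indirect bilirubin, ARC) no longer count. Parts B and C stay descriptive, in one table covering all visits. Safety data are still summarised in full.

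**The case against.** The strongest objection is that the blanks may not be in the protocol at all. They are empty cells in a table read from a PDF, and other cells in these tables look displaced. Table 1 shows vaccination marks under Weeks 2 and 12, while the text puts second doses at Days 29 and 57 (Weeks 4 and 8). The PK row of Table 5 is shifted against Table 1. All seven differing rows sit in the first part of Table 2, which could suit a page-level fault. This stands as a reason to check the source file. It does not dispose of the point: one identical gap across seven rows, beside rows that keep their Week 96 mark, is not what scattered misreads usually produce.

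The second objection is about coverage, and much of it stands. Body text covers vital signs, concomitant medications and the infusion site. Patients who stop treatment are asked to stay for follow-up visits and procedures (Section 6.3.3.1); one who stops in Part A and stays on the Table 1 visits has hematology and chemistry at each of them. A reader might infer that early stoppers have no laboratory or vital-sign record at discontinuation, or that their next sample is always 8 weeks off drug. The documents do not support either.

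The third is size, and it also stands. A reader might count nine lost Week 96 endpoints, but SAP Section 1.1 removes three. A reader might also see unmonitored rebound hemolysis in CAD. The withdrawal hemolysis in Section 4.3 was seen in 2 patients with PNH, and it shows no such harm here.

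**Conclusion.** The point holds as a conflict between Table 2, Table 6 and the stated Week 96 endpoints. As extracted, Table 2 schedules no hematology, chemistry, coagulation or urine sample at EOT/ET, and the text that governs sampling gives no firm substitute.

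The consequence is modest. Six tertiary, open-label, descriptive change endpoints lack a routine scheduled draw, and the last on-treatment safety laboratory values may be missing. No primary, key secondary or other tested endpoint relies on a Week 96 sample, and the primary endpoint counts treatment withdrawal as nonresponse whatever an ET sample would show. Since SAP Section 1.1 allows treatment only until 10 July 2024, the EOT/ET record for patients then on drug is probably the more useful part. The documents do not say how many patients could reach Week 96.

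It would go too far to say that the sponsor chose not to assess patients at this visit. Table 6 and the body text point to the opposite intent, so a table error is the likelier explanation. The conclusion assumes that the blanks are in the source file and that sites outside COVID-19 restrictions follow Table 2 as written. What sites actually collected cannot be known from these documents.

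**What to change.** 1. Check the Week 96 EOT/ET column of Table 2 in the source file. If the marks are there, the point closes.
2. If the blanks are real, reconcile Table 2 with Table 6 and Section 5.2.1.3: add the EOT/ET marks for hematology, serum chemistry, coagulation and urine studies, and for consistency with the body text also vital signs, concomitant medications and infusion-site assessment.
3. Notify sites, by letter or minor amendment, for any EOT/ET visits still to come. The documents do not show whether any remain.
4. For visits already held, state in the clinical study report which EOT/ET samples were taken, and give the number of patients behind each Week 96 summary.

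The cost is small. Table 2 already schedules blood at this visit for PK and antibodies, and the added tests are routine. The gain is a usable Week 96 change and a laboratory record at the end of treatment.
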